## 5. STATISTICAL METHODOLOGY

### 5.1. General Methodology

Unless otherwise noted, SAS® software (SAS Institute Inc, Cary, NC; Version 9.4 or later) will be used for the generation of all tables, graphs, and statistical analyses. Descriptive summaries for continuous variables will include, but not be limited to, the number of observations, mean, standard deviation, median, minimum, and maximum. Descriptive summaries for categorical variables will include the number and percentage of subjects in each category.

Interim analyses are planned for this study as defined in Section 10.

### 5.2. Treatment Groups

This is an open-label, dose-escalation/dose-expansion study of the LSD1 inhibitor INCB059872 as a monotherapy and combination therapy in subjects with advanced malignancies. The study will be conducted in 4 parts: Parts 1 and 2 will evaluate INCB059872 as monotherapy, with Part 1 for dose escalation and Part 2 for dose expansion, and Parts 3 and 4 will evaluate INCB059872 in combination with select therapies, with Part 3 for combination dose escalation and Part 4 for combination dose expansion.

For monotherapy, Parts 1 and 2 will be combined for summary purposes. Disease history and efficacy endpoints will be summarized by tumor types (AML, MF, MDS, SCLC, Ewing's sarcoma, poorly differentiated neuroendocrine, and other solid tumors). Within each tumor type, data will be summarized overall and by dose levels based on the dose regimen initially assigned. Summary tables for some tumor types may be replaced with listings when appropriate. For instance, an efficacy summary table for a cancer type may be replaced with a listing if this cancer type only contains a few subjects. All other data, including demographics, baseline disease characteristics, disposition, and safety, will be summarized separately for hematologic malignancies (TG A/A1/A2 combined as Group A) and solid tumor malignancies (TG B/B1/B2 combined as Group B). Within each group, data will be summarized overall and by dose levels based on the dose regimen initially assigned.

For combination therapy (Parts 3 and 4), all data in dose escalation and dose expansion will be combined and summarized by the following defined groups:

- Group C = TG C + TG C1;
- Group D = TG D + TG D1;
- Group E = TG E + TG E1.

Within each group, data will be summarized overall and by dose levels based on the dose regimen initially assigned.

In the event that several dose regimens tested are deemed substantially below the MTD, these doses may be combined for summary purposes.

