#### Monotherapy Dose Expansion (Part 2)

Upon identification of the recommended dose(s), up to 4 expansion cohorts per tumor type of approximately 15 subjects each may begin enrollment to further determine safety, tolerability, efficacy, PK, [REDACTED] of the selected dose(s). Treatment Group A1 will enroll subjects with AML or MDS and subjects in this cohort will have an opportunity to switch their treatment to a combination dose that is tested and found safe. Only subjects who have stable disease or better response for  $\geq 3$  months on monotherapy will be allowed to do so. Treatment Group A2 will enroll subjects with primary myelofibrosis (PMF) or secondary MF (post-polycythemia vera myelofibrosis [PPV-MF] or post-essential thrombocythemia myelofibrosis [PET-MF]). Treatment Group B1 will enroll subjects with SCLC. Treatment Group B2 will enroll subjects with Ewing's sarcoma and poorly differentiated neuroendocrine tumors. The selected doses for each treatment group are as follows:

- TG A1 dose will be 4 mg QD based on the safety and tolerability assessment in TG A.
- TG A2, TG B1, and TG B2 doses will be 3 mg QOD based on the safety and tolerability assessment in TG B (Part 1).

A study of the effect of food on the PK of INCB059872 will be conducted in Part 2, TG B1 only.

Note: Based on emerging data, the sponsor may decide to enroll specific subtypes of AML in TG A1.

If  $\geq 5$  subjects in the first 15 subjects of any cohort cumulatively (or more than 33% of subjects in cohorts

larger than 15 subjects) experience DLTs during Cycle 1, then further enrollment to the cohort will be stopped, and a lower dose level may be explored.

Individual dose titration will be permitted according to Protocol-defined safety parameters. Subjects will continue to receive INCB059872 in 28-day cycles until a withdrawal criterion is met.

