### 3.2. Subject Exclusion Criteria

A subject who meets any of the following criteria will be excluded from the study:

1. Receipt of anticancer medications, anticancer therapies, or investigational drugs within the following interval before the first administration of study drug (requirement may be waived with medical monitor approval):
  - a. < 5 half-lives or 14 days, whichever is longer, for any investigational agent
  - b. < 5 half-lives for all other anticancer medications
  - c. < 6 weeks for mitomycin-C or nitrosoureas
2. Any unresolved toxicity  $\geq$  Grade 2 from previous anticancer therapy except for stable chronic toxicities ( $\leq$  Grade 2) not expected to resolve.
3. All treatment groups: prior receipt of an LSD1 inhibitor therapy. Parts 3 and 4 TG E/E1: prior receipt of anti-PD-1, anti-PD-L1, or anti-PD-L2 antibody.
4. Any of the following laboratory results at screening without transfusions and hematopoietic growth factor support in solid tumors (no lower limits in AML and MDS, or in MF with medical monitor approval):

Laboratory Parameter	Value
Absolute neutrophil count ( $\times 10^9/L$ )	< 1.5
Hemoglobin (g/dL)	< 9.0
Platelet count ( $\times 10^9/L$ )	< 100

5. Laboratory and medical history parameters outside Protocol-defined range unless associated with primary malignancy or metastatic disease and with medical monitor approval:
  - a. Total bilirubin  $> 1.5 \times$  institutional upper limit of normal (ULN) if no liver metastases or  $> 3 \times$  ULN in the presence of liver metastases or presence of documented Gilbert syndrome (unconjugated hyperbilirubinemia).
  - b. Aspartate aminotransferase (AST) or alanine aminotransferase (ALT)  $> 2.0 \times$  institutional ULN.
  - c. Creatinine clearance  $< 60$  mL/min based on the institutional formula.
6. History or evidence of bleeding disorder requiring treatment.
7. History or presence of an abnormal ECG that in the investigator's opinion is clinically meaningful. A screening QTc interval  $> 470$  milliseconds, as corrected by Fridericia, is excluded. For subjects with an intraventricular conduction delay (QRS interval 120 milliseconds), the JTc interval may be used in place of the QTc with sponsor approval. Subjects with left bundle branch block are excluded.

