#### **4.1.2. Monotherapy Dose Expansion (Part 2)**

Upon identification of the recommended dose(s), up to 4 expansion cohorts per tumor type of approximately 15 subjects each may begin enrollment to further determine safety, tolerability, efficacy, PK, [REDACTED] of the selected dose(s). Treatment Group A1 will enroll subjects with AML or MDS (based on emerging data, the sponsor may decide to enroll specific subtypes of AML). Subjects in this A1 will have an opportunity to switch their treatment to a combination dose that is tested and found safe. Only subjects who have stable disease or better response for  $\geq 3$  months on monotherapy will be allowed to do so. Treatment Group A2 will enroll subjects with MF (PMF, PPV-MF, and PET-MF). Treatment Group B1 will enroll subjects with SCLC. Treatment Group B2 will enroll subjects with Ewing's sarcoma and poorly differentiated neuroendocrine tumors.

The selected doses for each treatment group are as follows:

- TG A1 dose will be 4 mg QD based on the safety and tolerability assessment in TG A (Part 1).
- TG A2, TG B1, and TG B2 doses will be 3 mg QOD based on the safety and tolerability assessment in TG B (Part 1).

A study of the effect of food on the PK of INCB059872 will be conducted in Part 2, TG B1 only.

If  $\geq 5$  subjects in the first 15 subjects of any cohort cumulatively (or more than 33% of subjects in cohorts larger than 15 subjects) experience DLTs during Cycle 1, then further enrollment to the cohort will be stopped, and a lower dose level may be explored.

Individual dose titration will be permitted according to Protocol-defined safety parameters. Subjects will continue to receive INCB059872 in 28-day cycles until a withdrawal criterion is met.

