### **5.1. Treatment Assignment**

#### **5.1.1. Subject Numbering and Treatment Assignment**

Study sites will enter subject demographic and baseline data into the Interactive Response Technology (IRT) in order to receive a subject number at the time of the subject enrollment. Sites will have to update the IRT system at each visit in order to receive the treatment allocation.

All subject numbers will be 6 digits; the first 3 digits will be the site number, and the last 3 digits will be the subject's number. This subject number will be maintained throughout the study and will not be reassigned. Subjects who withdraw consent or discontinue from the study after being assigned a subject number will retain their initial number.

This is a nonrandomized study; subjects will be assigned the same dose and treatment regimen in a particular treatment group. The investigator or designee will pull the correct number of bottles of study drug from their stock and dispense the study drug to the subject. All subsequent dispensing of study drug should follow this process. Refer to the IRT manual for detailed information.

For subjects who signed an ICF but are not allocated and for subjects who are allocated but were not treated, refer to the eCRF Completion Guidelines for instruction on which eCRFs to complete.

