Bone marrow examination (aspirate and biopsy) is required at screening for subjects with diseases that are typically monitored through bone marrow examination, including AML, MDS, and MF. Note: subjects with a history of allogenic hematopoietic stem cell transplantation should have bone marrow collected and analyzed locally for the purposes of determining disease status (where applicable); however their sample does not need to be processed for sequencing due to chimeric potential.

Data from the pathology report result from the bone marrow examination will be captured in the eCRF. All bone marrow examinations should include a unilateral aspiration and biopsy with FISH and cytogenetic testing, when feasible and indicated. Subjects may be enrolled based on a biopsy only when a "packed marrow" precludes aspiration at the decision of the medical monitor. Results of assessments performed under standard of care before the signing of informed consent may be used as the baseline disease assessment in lieu of a study-specific procedure if performed within 60 days of the first dose of study drug (Cycle 1 Day 1) and if adequate archive material is available and there has been no anticancer therapy in the interim.

For disease assessment timepoints in AML, MDS, and MF that do not correspond to a bone marrow examination, peripheral blood myeloid blast percentage will be evaluated by microscopic evaluation or other appropriate methodology and will be used as appropriate in conjunction with other parameters (eg, cytopenias) in determining disease status.

For AML and MDS subjects, a bone marrow disease assessment is strongly encouraged during Cycle 2, preferably at Cycle 2 Day 1 for subjects who have a significant circulating blast count reduction (as determined by the investigator), including subjects who are not completely cleared of circulating blasts; a bone marrow biopsy and/or aspirates for response is to be performed at Cycle 4 Day 1 or earlier as clinically indicated, followed by every other month as clinically indicated, or upon circulating blood cell recovery to assess antileukemic activity (cytogenetic testing is not required if CR is not presented). Bone marrow examination schedule can be modified with approval from the medical monitor.

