### 7.1. General Considerations

For subjects with solid tumors, AML, and MDS, the proportion of subjects who meet the response criteria as appropriate for the tumor type will be summarized with descriptive statistics.

For MF subjects, changes and percentage changes in spleen volume from baseline to Week 12 [REDACTED] will be summarized descriptively. All efficacy analyses will be performed using the FAS.

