### **7.3.2.2. Best Overall Response and Objective Response Rate**

#### **7.3.2.2.1. Altering the Natural History of the Disease**

For AML, BOR based on altering the natural history of the disease is the best response recorded before and including the first progression, which consists of treatment failure, relapse, and PD, in the order of CR, CRI, MLFS, PR, peripheral blood blast response, SD, and progression. In the case of SD, measurements must meet the SD criterion at least once on or after Day 24.

A subject is considered a responder if the subject has a BOR of CR or CRI.

Objective response rate is defined as the proportion of responders based on altering the natural history of the disease. Subjects who do not have sufficient baseline or on-study response assessment information to be adequately assessed for response status will be included in the denominators in the calculations of ORR.

Best overall response will be summarized descriptively. Objective response rate will be estimated with its 95% CI. Confidence intervals will be calculated based on the exact method for binomial distributions.

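### Responses first reached after a TG A1 subject switches to a combination would be counted in the monotherapy response rate

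*SAP*

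**What the plan says.** The Protocol (Synopsis and 4.1.2) says of TG A1 that "subjects in this cohort will have an opportunity to switch their treatment to a combination dose that is tested and found safe". The condition follows: "Only subjects who have stable disease or better response for" at least 3 months on monotherapy. SAP Section 3 repeats the option without the 3-month condition and attaches no analysis rule to it.

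SAP 5.2 pools Parts 1 and 2 and reports efficacy by tumor type: "Within each tumor type, data will be summarized overall and by dose levels based on the dose regimen initially assigned". It defines Group C as TG C plus C1 and Group D as TG D plus D1; A1 switchers appear in neither. On the population, SAP 7.1 states: "All efficacy analyses will be performed using the FAS".

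For AML, SAP 7.3.2.2.1 says best overall response "is the best response recorded before and including the first progression, which consists of treatment failure, relapse, and PD", and a responder has CR or CRi. For MDS, SAP 7.3.3.2.1 uses the same construction, with progression also covering disease transformation, and a responder has CR. Neither definition mentions the switch or the start of a second agent.

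**The concern.** The Parts 1 and 2 secondary objective (SAP 2.2.2) is antitumor activity of INCB059872 given alone. If the response window stays open after a second agent starts, the reported rate mixes monotherapy responses with responses to two drugs, and the reader cannot separate them in the table.

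Best response is a maximum over the window, so extending the window past the switch can leave the response rate unchanged or raise it, never lower it.

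Safety has a parallel problem. Under SAP 9.2.1 the treatment-emergent window runs to 30 days after the last study treatment, and SAP 5.2 tabulates Group A safety by initial regimen. Events that began on the combination therefore enter the Group A all-cause tables unmarked.

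**Working it through.** **1. Do switchers stay in the monotherapy tables?** SAP 5.2 assigns by initial regimen, and Groups C and D contain only their own treatment groups. Switchers could not be entered there as new subjects either. Protocol 3.2 excludes, for "All treatment groups: prior receipt of an LSD1 inhibitor therapy", and Protocol 5.1.1 says of the subject number: "This subject number will be maintained throughout the study and will not be reassigned". SAP 4.1.1 and 4.1.3 tie Day 1 and baseline in Parts 1 and 2 to the first INCB059872 dose, with no reset.

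**2. Is the response window open at the switch?** The condition is stable disease or better, so progression has not occurred and the window is open.

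**3. Will assessments fall on the combination?** Disease assessment is every 4 weeks (SAP 7.3.2.1, 7.3.3.1). Under Protocol 7.6, a marrow "for response is to be performed at Cycle 4 Day 1 or earlier as clinically indicated, followed by every other month" as clinically indicated.
- Cycle 4 Day 1 = 3 × 28 + 1 = Day 85.
- Two 28-day cycles later = 85 + 56 = Day 141.
- Three months is about 91 days.

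With a switch at about Day 91, the Day 85 marrow is on monotherapy and the next, at about Day 141, is on the combination.

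**4. The plan's own figure.** The only numerical basis for a cohort of 15 is the chance of seeing at least one toxicity at a true rate of 15%: 1 − 0.85^15 = 0.913, which agrees with the stated 90% or more. No target is given for the response rate.

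**5. Size per misattributed responder.** The shift is 100/n points. Intervals are exact (Clopper-Pearson) 95%, the method the SAP specifies.

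| Row size n | Without the extra responder | With one post-switch first responder | Shift (points) |
|---|---|---|---|
| 15 | 0/15 = 0% (0 to 21.8) | 1/15 = 6.7% (0.2 to 31.9) | 6.7 |
| 15 | 1/15 = 6.7% (0.2 to 31.9) | 2/15 = 13.3% (1.7 to 40.5) | 6.7 |
| 10 | 1/10 = 10.0% (0.3 to 44.5) | 2/10 = 20.0% (2.5 to 55.6) | 10.0 |
| 18 | 1/18 = 5.6% (0.1 to 27.3) | 2/18 = 11.1% (1.4 to 34.7) | 5.6 |

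The row sizes are illustrations. A1 is planned at about 15; 18 adds the 3 Part 1 subjects at 4 mg QD (Protocol 1.6.2); 10 is an assumed AML-only row.

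**6. How many might there be?** The documents do not say. At the July 2017 cutoff (Protocol 1.6.2), 6 of 39 subjects had been treated for more than 90 days; 15 × 6/39 = 2.3 as a rough guide to how many of 15 might reach the earliest switch time. Assume 2 switchers and a post-switch response rate between 10% and 27.8%. These are azacitidine-alone figures from Protocol 1.3.2, in chemotherapy-resistant and newly diagnosed AML respectively, and the first includes hematologic improvement.
- Expected extra responders: 2 × 0.10 = 0.20 to 2 × 0.278 = 0.56.
- Chance of at least one: 1 − 0.90² = 19% to 1 − 0.722² = 48%.
- Expected inflation at n = 15: 0.20/15 = 1.3 points to 0.556/15 = 3.7 points.

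**The case against.** The strongest reply is that the SAP is silent on switchers, and that grouping by initial regimen is an ordinary convention meant for dose changes. It is ordinary for dose changes. Here, however, a second agent is added, and the stated grouping and best-response rules, applied literally, do classify the later response as monotherapy.

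Some subsections of SAP 7.3.2 and 7.3.3 are redacted, and a rule could sit there. The best-response and response-rate definitions themselves are readable and contain no cut. Nor does the Protocol's stop at new antineoplastic therapy (6.4.2) help: it governs follow-up of subjects who have discontinued treatment.

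Several limits do stand. Day 91 is the earliest reading of the 3-month condition, and later marrows are as clinically indicated and can be rescheduled, so Day 141 is one scenario. Because SAP 5.2 separates AML from MDS and pools Parts 1 and 2, n = 15 need not be an actual table row. The planned listings might allow reconstruction, and Appendix A plans tables of events attributed to ATRA, azacitidine or nivolumab, but neither corrects the reported rate or splits the all-cause tables by onset.

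The proposed cut also has a cost: a remission that was developing on monotherapy but first documented after the switch would leave the numerator.

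**Conclusion.** The concern holds. On the visible rules, a CR/CRi (AML) or CR (MDS) first reached after the switch is reported as a monotherapy response, and the error runs in one direction.

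The rule gap is clear; its numerical effect is not. It depends on the number of switchers, which may be zero, on how many were not already responders at the switch, and on their response on the combination. The intervals overlap widely at these sizes. What is at issue is bias in the point estimate and what the responders represent. All analyses are exploratory and no stopping rule uses A1 data. The SAP should be changed, but no formal decision turns on it.

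**What to change.** **Efficacy.** In SAP 5.2, 7.3.2.2.1 and 7.3.3.2.1, state that for TG A1 subjects who switch, monotherapy best response and response rate use only assessments before the first dose of the combination agent. Keep these subjects in the denominator with their pre-switch best response. Report the number of switchers and list post-switch responses separately, so that a remission documented late remains visible.

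**Safety.** Keep the full treatment-emergent window (9.2.1) and the INCB059872 exposure definition (6.4.1). Flag events with onset on or after the first combination-agent dose, and show those events and post-switch exposure separately. Flagged events still need reading in context, because switchers may continue INCB059872.

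**Cost.** SAP wording, one flag and a few listings. Appendix A already plans response by visit (Listing 2.6.1), drug administration (2.7.1) and adverse events (2.7.2). The CRF is not among the documents, so confirm that it captures the date of the first combination-agent dose for A1 subjects. The monotherapy rate may come out slightly lower.

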## **5.3. Analysis Populations**

### **5.3.1. Full Analysis Set**

The FAS includes all subjects enrolled in the study who received at least 1 dose of INCB059872, ATRA, azacitidine, or nivolumab.

The FAS will be used for the summary of demographics, baseline characteristics, subject disposition, and analyses of all efficacy data.

### **5.3.2. Safety Population**

The safety population includes all enrolled subjects who received at least 1 dose of INCB059872, ATRA, azacitidine, or nivolumab.

All safety analyses will be conducted using the safety population.

### **5.3.3. Pharmacokinetic Evaluable Population**

The PK-evaluable population includes all subjects who received at least 1 dose of study treatment and provided at least 1 postdose sample (1 PK measurement). The study pharmacokineticist will review data listings of study drug administration and sample records to identify subjects to be excluded from analyses of PK data.

## **6. BASELINE, EXPOSURE, AND DISPOSITION VARIABLES AND ANALYSES**

[Appendix A](#) provides a list of data displays. Sample data displays are included in a separate document.

### **6.1. Baseline and Demographics, Physical Characteristics, and Disease History**

#### **6.1.1. Demographics and Baseline Characteristics**

The following demographics will be summarized for the FAS: age, sex, race, ethnicity, weight, height, BMI, and BSA (TGs C/C1 and TGs D/D1). Size of spleen and liver by manual palpation (for subjects with MF as applicable), and ECOG performance status at baseline will be summarized and listed for the FAS.

#### **6.1.2. Disease History**

For AML subjects in the FAS, time since initial diagnosis, AML disease category, current WHO classification, French-American-British classification, European LeukemiaNET risk classification, presence of extramedullary disease, FLT3 status, IDH1 status, and IDH2 status will be summarized and listed.

For MDS subjects in the FAS, time since initial diagnosis, current WHO classification, current IPSS-R group for MDS, and current IPSS-R prognostic variable for cytogenetics will be summarized and listed.

For MF subjects in the FAS, time since initial diagnosis, current MF disease category, availability of bone marrow biopsy result, prior medications for MF, prior splenic irradiation, transfusion dependence per protocol definition, prognostic factors, IWG risk level, and JAK2 status will be summarized and listed.

For SCLC subjects in the FAS, time since initial diagnosis, stage at initial diagnosis, current stage of disease, current sites of disease, MYC rearrangement status, and PD-L1 status will be summarized and listed.

For Ewing's sarcoma subjects in the FAS, time since advanced/metastatic diagnosis, stage at initial diagnosis, grade at initial diagnosis, sites of disease at initial diagnosis, current stage of disease, current sites of disease, cytogenetics status, CDKN2A status, TP53 status, and STAG2 status will be summarized and listed.

For subjects with poorly differentiated neuroendocrine in the FAS, time since initial diagnosis, stage at initial diagnosis, current stage of disease, current sites of disease, MYC rearrangement status, and PD-L1 status will be summarized and listed.

For subjects with other solid tumors in the FAS, time since initial diagnosis, stage at initial diagnosis, current stage of disease, solid tumor cancer type, current sites of disease, MYC rearrangement status, and PD-L1 status will be summarized and listed.

Time since diagnosis will be calculated as follows:

$$\text{Time since diagnosis (years)} = (\text{Day 1 date} - \text{date of diagnosis} + 1) / 365.25.$$

